## 19.5. ECG EVALUATIONS

The Investigator’s judgment of overall assessment of ECG (Normal, Abnormal, Not Clinically Significant [ANCS], and Abnormal, Clinically Significant [ACS]) will be recorded at baseline and end of study. A summary of shift from baseline to end of study in overall assessment will be provided.

## 19.6. VITAL SIGNS

The following Vital Signs measurements will be reported for this study:

- Sitting Systolic Blood Pressure (mmHg)
- Sitting Diastolic Blood Pressure (mmHg)
- Sitting Heart Rate (bpm)
- Weight (kg)
- Height (cm) (at Screening only)
- BMI (kg/m^2) (calculated automatically by the EDC system)

The following summaries will be provided for vital signs data: Observed and change from baseline by visit.

### 19.6.1. VITAL SIGNS SPECIFIC DERIVATIONS

Blood pressure is taken twice five minutes apart at each vital sign collection. Blood pressure will be analyzed as the average of these two measurements. If there is only 1 measurement, that measurement will be used.

## 19.7. PHYSICAL EXAMINATION

Abnormalities in physical examinations will be presented in a listing.

## 19.8. PHARMACOKINETICS

Descriptive statistics for concentrations of bempedoic acid and its metabolite ESP15228 will be presented for each visit weeks 4, 8, and 12 if the PK sample time is within 18-30 hours of the last dose of IMP. All concentration data will also be presented in a listing. All concentrations below the limit of quantification or missing data will be labelled as such in the concentration data listings. Concentrations below the lower limit of quantification will be treated as zero in summary statistics.

[REDACTED]

Version Number: 1.7  
 Version Date: 21Mar2018

[REDACTED]

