
Criteria for evaluation:
 
Efficacy:
 
Lipid and Cardiometabolic Assessments:
 
• Calculated LDL-C, HDL-C, non-HDL-C, TC, TG, apoB, and hs-CRP
– If TG exceeds 400 mg/dL (4.5 mmol/L) or LDL-C is \leq50 mg/dL (1.3 mmol/L), direct measure of LDL-C will be conducted.

Safety:

Safety Assessments:

Adverse events and SAEs will be collected and reported. Clinical endpoints will be collected and adjudicated by an independent CEC. Other safety assessments will include clinical safety laboratories (including hematology, blood chemistry, coagulation, HbA_{1C}, fasting glucose, and urinalysis), physical examination (PE) findings, vital signs, electrocardiogram (ECG) readings, and weight.

Clinical Laboratory Assessments:

- Hematology: Hematocrit (Hct), Hgb, mean corpuscular hemoglobin (MCH), mean corpuscular hemoglobin concentration (MCHC), mean corpuscular volume (MCV), platelet count, red blood cell (RBC) count, white blood cell (WBC) count with differential (absolute values only)
- Urinalysis (Dipstick): Clarity, bilirubin, color, glucose, ketones, leukocyte esterase, nitrite, occult blood, pH, protein, specific gravity, urobilinogen
- Urinalysis (Microscopic): Obtain centrally only if positive urine dipstick; bacteria, casts, crystals, epithelial cells, RBC, and WBC
- Coagulation: Prothrombin time (PT) and International Normalized Ratio (INR)
In patients receiving anticoagulant therapy PT/INR must be evaluated at Visit T1 and 3 to 5 days post Visit T1 using local or central lab
- Serum Chemistry (fasting): Albumin (ALB), alkaline phosphatase (ALK-P), ALT (or serum glutamic pyruvic transaminase [SGPT]), AST (or serum glutamic oxaloacetic transaminase [SGOT]), blood urea nitrogen (BUN), calcium (Ca), carbon dioxide (CO₂), chloride (Cl), creatinine, CK, glucose, lactate dehydrogenase (LDH), phosphorus, potassium (K), sodium (Na), total and direct bilirubin, total protein, uric acid
- HbA_{1C}

Other Screening Laboratories:

- Serum pregnancy test (only for females who are of childbearing potential) with urine pregnancy test at T1, FSH (naturally postmenopausal females <55 years of age at screening and >1 year without menses)
- HBsAg, hepatitis C virus (HCV)
- TSH

Other Assessments:

- Trough plasma concentrations of bempedoic acid and its metabolite ESP15228 will be collected before dose at Weeks 4, 12, and 24

Safety and Monitoring:

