Clinical endpoints using standardized definitions will be adjudicated by an independent blinded expert CEC for all ongoing Phase 3 studies in the bempedoic acid program. Investigator-reported clinical endpoints and adjudicated clinical endpoints will be summarized by event type and treatment group. Additional details regarding the clinical endpoints and their definitions will be included in CEC Charter.

Pharmacokinetics

Three pharmacokinetic (PK) samples will be collected. Plasma concentrations of bempedoic acid and its metabolite ESP15228 will be determined in patients who are receiving bempedoic acid, who have compliance $\geq 80\%$, and who have taken a dose of bempedoic acid within 2 days of the sample collection. All patients, site personnel, and study personnel will remain blinded to treatment assignment throughout the duration of the study. Personnel performing the bioanalytical analysis of bempedoic acid concentrations will be unblinded in order to assay the appropriate samples during the study. Plasma concentrations of bempedoic acid and ESP15228 will be summarized using descriptive statistics by time point.

TABLE OF CONTENTS

1.	TITLE PAGE.....	1
2.	SYNOPSIS	2
3.	ABBREVIATIONS AND DEFINITIONS.....	20
4.	INTRODUCTION.....	25
4.1.	Overview of the Disease Under Study.....	25
4.2.	Overview of Bempedoic Acid	26
4.2.1.	Mechanism of Action	26
4.2.2.	Pharmacokinetics and Pharmacology	26
4.2.3.	Dose Selection	27
4.3.	Nonclinical Experience.....	27
4.4.	Clinical Experience.....	27
5.	STUDY OBJECTIVES AND ENDPOINTS.....	29
5.1.	Study Objectives	29
5.1.1.	Primary Objective	29
5.1.2.	Secondary Objectives	29
5.1.3.	Tertiary Objective.....	29
5.2.	Study Endpoints.....	29
5.2.1.	Primary Endpoint.....	29
5.2.2.	Secondary Endpoints	29
5.2.3.	Tertiary Endpoints	29
5.2.4.	Safety Endpoints.....	30
6.	INVESTIGATIONAL PLAN.....	30
6.1.	Overall Study Design.....	30
6.2.	Study Population and Selection.....	30
6.2.1.	Inclusion Criteria	31
6.2.2.	Exclusion Criteria	33
6.3.	Patient Identification, Randomization, and Blinding	36

7.	INVESTIGATIONAL MEDICINAL PRODUCT	38
7.1.	Investigational Medicinal Product Supply and Control.....	38
7.2.	Administration of Investigational Medicinal Product	38
7.3.	Concomitant Medications	39
7.3.1.	Lipid-Regulating Medications and Supplements.....	39
7.3.2.	Prohibited Medications	40
7.3.3.	Allowable Medications	41
7.4.	Patient Lifestyle and Dietary Guidelines.....	41
7.5.	Treatment Compliance.....	41

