8.3.6. Treatment Week 8 Phone Call (Visit T3; Day 57 ±3 days)

Patients will undergo the following assessments via telephone at Week 8 (Visit T3):

1. Concomitant medication review (ongoing)
2. Assess AEs, SAEs, and potential clinical endpoints
3. Diet and exercise counseling
4. Assessment of study drug dosing adherence

Note: If the patient discontinues at or between study visits, please proceed to [Section 8.4.1](#) for detailed instructions.

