8.3.8. Treatment Week 24/EOS (Visit T5; Day 169 ±7 days)

Patients will undergo the following assessments and procedures at Week 24 (Visit T5):

1. Concomitant medication review (ongoing)
2. Assess AEs, SAEs, and potential clinical endpoints (ongoing)
3. Weight
4. Vital signs
5. Central clinical laboratory evaluations:
 - Hematology, blood chemistry, and urinalysis
 - apoB
 - hs-CRP
 - HbA_{1C}
 - Basic fasting lipids (TC, calculated LDL-C, HDL-C, non-HDL-C, and TG)
 - PK Sample before dose
6. Return of study drug; assessment and recording of dosing adherence
7. IWRS contact to terminate the subject or register completion
8. Physical Exam
9. 12-Lead ECG

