8.4.1. Procedures for Early Withdrawal

If a patient withdraws or is removed from the study for any reason, all "End of Study" procedures should be completed. Reason for withdrawal, date of the discontinuation, and date of the last dose of study drug should be recorded in the appropriate section of the eCRF.

Additionally, the discontinuation visit date must be registered in IWRS. Study drug assigned to the withdrawn patient may not be assigned to another patient.

All effort should be made to have each patient complete all study visits on schedule according to the protocol. Accommodations for early or late visits in special circumstances will be considered by the Sponsor to prevent early withdrawal. Written notice (regardless of cause) is to be provided within 48 hours of the withdrawal to the Sponsor personnel or the Medical Monitor. At the time of discontinuation, every effort should be made to ensure all relevant procedures and evaluations scheduled for the final study visit are performed.

Patients choosing to withdraw from the study early should be encouraged to return for all study scheduled clinic visits even if they are no longer taking IMP. Patients who withdraw from all aspects of the study will be asked to consent to clinical visits or phone calls for safety assessments, including AEs, concomitant medication, and current health status through Week 24 (Visit T5). Subjects who are unwilling to return for clinic visits should return for an end of study visit (Visit T5).

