10.1.6.2. Clinical Laboratory Tests (PK)

A PK blood sample will be collected prior to dosing at Visits T2, T4, and T5.

Patients will be in a seated position during the blood collection. Collection schedule and instructions are provided in the Clinical Laboratory Manual. A description of the sample collection, storage, and shipping are described in [Section 10.1.6.3](#).

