### 3. STUDY DESIGN

#### 3.1. GENERAL DESCRIPTION

This is a Phase 3, randomized, double-blind, placebo-controlled, parallel group multicenter study that will be conducted at approximately 71 clinical sites in North America. Screening Week -5 (Visit S1) will be approximately 5 weeks prior to randomization. Eligible patients will return to the clinical site at Week -4 (Visit S2) to initiate administration of single-blind (patient only) placebo study drug. Eligible patients will return at Week -1 (Visit S3) for lipid and safety laboratories and an assessment of tolerability and study drug adherence. Approximately 300 patients with a history of statin intolerance (SI) will be stratified based on patient type (primary prevention; secondary prevention) and randomized at Week 0 (Visit T1) in a 2:1 ratio to receive either bempedoic acid 180 mg (n = 200) or matching placebo (n = 100) once daily for 24 weeks. Randomized patients will return for clinic visits at Week 4 (Visit T2), Week 12 (Visit T4), and Week 24 (Visit T5). A phone visit will occur at Week 8 (Visit T3).

Figure A 1002-046 Study Design

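### SAP 19.8 summarises PK concentrations at Weeks 4, 8 and 12, but samples are scheduled at Weeks 4, 12 and 24, so as written Week 24 gets no summary statistics

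*SAP*

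**What the plan says.** SAP 19.8 (Pharmacokinetics) states that descriptive statistics for the two analytes "will be presented for each visit weeks 4, 8, and 12 if the PK sample time is within 18-30 hours" of the last dose of study drug. The same section sends every concentration to a listing.

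The sampling schedule is set in the protocol. The synopsis (Other Assessments) says trough concentrations "will be collected before dose at Weeks 4, 12, and 24". Section 10.1.6.2 says "A PK blood sample will be collected prior to dosing at Visits T2, T4, and T5". The visit lists for T2, T4 and T5, Table 2 and Appendix 1 agree; for T5 (Week 24), section 8.3.8 lists "PK Sample before dose".

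Week 8 is not a clinic visit. Protocol 8.3.6 opens with "Patients will undergo the following assessments via telephone at Week 8 (Visit T3" and lists medication review, adverse events, counselling and adherence, with no blood draw. SAP 3.1 says the same: "A phone visit will occur at Week 8 (Visit T3".

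On the intended summary, the protocol synopsis (Pharmacokinetics) plans three samples per patient and says the concentrations "will be summarized using descriptive statistics by time point". Protocol 11.1 gives the SAP precedence where the two documents differ on data analysis.

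**The concern.** The SAP's list includes a week at which nobody is scheduled to be bled and leaves out a week at which everyone still attending is. It conflicts with the protocol schedule and with the SAP's own design section.

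At stake is the only scheduled PK draw after Week 12, in a trial whose secondary objectives include 24-week safety and tolerability. A programmer following 19.8 to the letter would produce no Week 24 mean, spread or range for either analyte. The Week 8 column would be empty, or would hold only a few off-schedule samples presented as if they were a planned time point.

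**Working it through.** The plan states no figure to reproduce here. The check compares two lists of weeks.

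**1. Visits to weeks** (SAP 3.1): T2 = Week 4, T3 = Week 8 (phone), T4 = Week 12, T5 = Week 24.

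**2. Side by side**

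| Week | Visit | PK sample scheduled (protocol) | Descriptive statistics planned (SAP 19.8) |
|---|---|---|---|
| 4 | T2 | yes | yes |
| 8 | T3, phone | no | yes |
| 12 | T4 | yes | yes |
| 24 | T5 | yes | no |

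Scheduled {4, 12, 24} against summarised {4, 8, 12}: the overlap is {4, 12}. Week 8 is summarised but not scheduled, and Week 24 is scheduled but not summarised. The SAP covers 2 of the 3 scheduled time points.

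**3. Count of outputs.** Planned summaries: 3 weeks × 2 analytes = 6, of which 1 × 2 = 2 (Week 8) have no scheduled sample. Scheduled analyte-by-week sets: 3 × 2 = 6, of which 1 × 2 = 2 (Week 24) get no statistics.

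**4. Could a scheduled draw be assigned to Week 8 by visit windowing?** The draw days in protocol Table 2 are:

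- T2: 29 ± 3 = Days 26–32
- T4: 85 ± 3 = Days 82–88
- T5: 169 ± 7 = Days 162–176

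The header row of the SAP 6.4 window table is missing from the supplied text. Reading the windows in visit order (an assumption), those after Day 1 are Week 4 [2, 43], Week 8 [44, 71], Week 12 [72, 127] and Week 24 [128 onward]. The latest T2 draw falls 44 − 32 = 12 days before the Week 8 window opens, and the earliest T4 draw falls 82 − 71 = 11 days after it closes. No scheduled draw can enter Week 8, and every T5 draw lands in Week 24. Whether these windows apply to PK samples is not visible in the supplied text; the mismatch in step 2 does not depend on them.

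**5. Does other text repair it?** The synopsis would support a Week 24 summary, but Protocol 11.1 lets the SAP prevail on analysis. Protocol 11.8 covers listings and a separate population PK report and does not specify a Week 24 summary. No other supplied SAP section adds one, and the addendum's table list contains no PK output. Nor is this a remnant of the protocol amendment: the superseded schedule had an extra PK sample on Day 1, not at Week 8.

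**The case against.** The strongest reply is that this is an editorial slip with little practical effect. SAP 3.2 adopts the protocol's schedule of events, and SAP 3.1 makes Week 8 a phone visit, so anyone building the table would notice that the week has no scheduled data. SAP 8 leaves the format and content of tables to separate templates, which are not supplied and may already show the right weeks. The modification history also records a dry run of this study's outputs before version 1.7. All of that is fair: the mismatch in the text is certain, but its effect on the actual table is not. The dry run does not settle it either, because the wording is still in version 1.7.

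A second reply is that Week 8 need not be empty. Protocol 8.4.1 asks for end-of-study procedures "If a patient withdraws or is removed from the study for any reason", so a PK sample could be drawn between scheduled visits. That is possible, but such samples would be incidental, would count only if taken 18–30 hours after the last dose, and would not replace the Week 24 summary.

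A third is that correcting the weeks leaves another difference open. SAP 19.8 selects samples by the 18–30 hour rule, whereas the synopsis uses compliance of at least 80% and a dose within 2 days of sampling. Those passages also need to be reconciled, but that is a separate matter and does not affect this one.

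**Conclusion.** SAP 19.8 is wrong as written: the weeks to be summarised do not match the weeks sampled. A slip in the labels is the natural reading, since a deliberate decision to omit Week 24 would not explain adding a phone visit.

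The consequence is small. Two of the six scheduled analyte-by-week sets would be listed without statistics if the text is followed literally. The number of Week 24 samples affected cannot be derived from the documents; it is at most the 200 patients planned for bempedoic acid, less discontinuations and samples outside the 18–30 hour limit. No data are lost, and no inferential analysis or safety summary changes. The mismatch rests only on the stated schedules. Its effect on output assumes that the table shell follows 19.8, which could not be checked.

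**What to change.** In SAP 19.8, replace the listed weeks with Weeks 4, 12 and 24, and check that the PK table shell shows the same three. All 3 scheduled time points would then be summarised instead of 2.

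The cost is one phrase and one shell check, with no change to data collection. The December 2018 SAP addendum reports that the planned analyses were complete, so the change may have to be recorded as a dated correction or addendum; if the issued PK table followed the current wording, a Week 24 summary would need to be added to it.

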## 20. DATA NOT SUMMARIZED OR PRESENTED

The other variables and/or domains not summarized or presented are:

- Comments
- Variables used by the data entry system to direct user to proper page (e.g., patient visit status, patient health status)
- Inclusion/Exclusion Criteria that are not violated
- Normal Physical Examination Results
- Diet and Exercise Counselling
- Normal PE findings

These domains and/or variables will not be summarized or presented, but will be available in the clinical study database, SDTM and/or ADaM datasets.

## APPENDIX 1. PROGRAMMING CONVENTIONS FOR OUTPUT

### Quintiles Output Conventions

File names should only consist of uppercase letters, lowercase letters, digits (0 to 9) and underscores. A period should only be used to indicate a separator between the file name and the extension. No spaces, other special characters or punctuation marks are permitted.

As far as possible, output files should be in RTF format, although .DOC files are also permitted.

The program, program log and output file name should reflect the type and number of the statistical output. If this is not possible, then the output name should be at least as descriptive as possible. A prefix can be used to distinguish between a Table, Listing and Figure document ('T' for table, 'L' for listing and 'F' for figure). If there is only 1 digit in the number of the table, listing or figure in the place where 2 digits are possible, a leading zero should be added in the file name to make sorting consistent with the sequence (eg T14\_3\_01\_1.RTF).

### PAPER SIZE, ORIENTATION AND MARGINS

The size of paper will be Letter for the United States, otherwise A4.

The page orientation should preferably be landscape, but portrait is also permitted.

Margins should provide at least 1 inch (2.54 centimeters) of white space all around the page, regardless of the paper size.

The number of columns per page (linesize) should be 145 for A4 and 134 for Letter.

The number of rows per page (pagesize) should be 49 for A4 and 51 for Letter.

---

Version Number: 1.7  
Version Date: 21Mar2018

## FONTS

The font type ‘Courier New’ should be used as a default for tables and listings, with a font size of 8. The font color should be black. No **bolding**, underlining *italics* or subscripting should be permitted. Try to avoid using super-scripts, unless absolutely necessary. Single spacing should be used for all text. Figures should have a default font of “Times Roman”, “Helvetica”, or “Courier New” .

This can be achieved by using the following options in SAS:

```
goptions
gunit = pct
cback = white
colors = (black)
hby = 2.4
ftext = "TimesRoman"
htext = 2.5
device = cgmof97l
gaccess = gsasfile;
filename gsasfile "....cgm";
```

## HEADER INFORMATION

Headers should be defined as follows:

- The header should be placed at the top of the page (same place on each page) regardless of the size or orientation of the table or listing
- The customer name and protocol number should appear in row 1, left-aligned
- The output identification number should appear in row 2, centered
- The output title should start in row 3, centered
- The output population should appear in row 4, centered. The population should be spelled out in full, e.g. Intention-to-Treat in preference to ITT.
- Row 5 should be a continuous row of underscores (‘\_’) (the number of underscores should equal the linesize)
- Row 6 should be a blank line
- Mixed case should be used for titles
- The output titles should be designed so that they are arranged consistently through all outputs. For example, content (eg Vital Signs) followed by metric (eg Change from Baseline) e.g. Vital Signs – Change from Baseline.
- Titles should not contain quotation marks or footnote references
- The column headings should be underlined with a row of underscores (‘\_’)
- Column headings spanning more than one column should be underlined and have underscores on either side of the title and should be centered
- Column headings containing numbers should be centered
- Column headings should be in sentence case
- In general, the population count should appear in the column header in the form “(N=XXX)”

[REDACTED]

Version Number: 1.7  
 Version Date: 21Mar2018

[REDACTED]

- “Statistic” should be the column header over n, Mean, SE, n (%) etc.
- As a rule, all columns should have column headings.

[figure not shown]
**TABLE AND LISTING OUTPUT CONVENTIONS**

General:

- The first row in the body of the table or listing should be blank
- The left hand column should start in column 1. No indenting or centering of the output should occur.
- Rounding should be done with the SAS function ROUND.
- Numbers in tables should be rounded, not truncated.
- Alphanumeric output should be left aligned.
- Numbers should be decimal point aligned.
- Whole numbers should be right aligned.
- Text values should be left aligned.
- The first letter of a text entry should be capitalized
- Listings of adverse events, concomitant medications, medical histories etc. should be sorted in chronological order, with earliest adverse event, medication or history coming first.
- The study drug should appear first in tables with treatments as columns
- In general, only present totals (across treatment groups) at baseline/randomization, and do not present them post randomization, unless the customer specifically requests it.
- If possible, include 100% frequencies in the table shell, so that it is clear what the denominator is for percentage calculations.
- All listing outputs should be sorted (preferably by Treatment, Site Number and Subject Number).
- Do not use superscripts and subscripts
- Exponentiation will be expressed using a double asterisk, i.e., mm3 will be written as mm\*\*3.
- All variables that are output in the CRF (which have data present) should appear in the listings, along with all derived data appearing in the corresponding tables
- The width of the entire output should match the linesize

Univariate Statistics:

- Statistics should be presented in the same order across tables (i.e., n, Mean, SD, Q1, Median, Q3, Minimum, Maximum)
- Table statistics should line up under the N part of the (N=XXX) in the table header. All decimal points should line up. If the minimum and maximum are output on one line as Minimum, Maximum then the comma should line up with the decimal point.
- If the original data has N decimal places, then the summary statistics should have the following decimal places:  
 Minimum and maximum: N  
 Mean, median and CV%: N + 1  
 SD: N + 2

Version Number: 1.7  
 Version Date: 21Mar2018

Frequencies and percentages (n and %):

- Percent values should be reported inside parentheses, with one space between the count and the left parenthesis of the percentage. Parentheses should be justified to accept a maximum of 100.0 as a value and padded with blank space if the percent is less than 100.0. An example is given below:  
 77 (100.0%)  
 50 ( 64.9%)  
 0 ( 0.0%)
- Percentages will be reported to one decimal place, except percents <100.0% but >99.9% will be presented as '>99.9%' (e.g., 99.99% is presented as >99.9%); and percents < 0.1% will be presented as '<0.1%' (e.g., 0.08% is presented as <0.1%). Rounding will be applied after the <0.1% and >99.9% rule.  
 Eg ( <0.1%)  
 ( 6.8%)  
 (>99.9%)  
 Percentages may be reported to 0 decimal places as appropriate (for example, where the denominator is relatively small).
- Where counts are zero, percentages of 0.0% should appear in the output.

Confidence Intervals:

- As a rule confidence intervals are output to one place more than the raw data, and standard deviations and standard errors to two places more than the raw data
- Confidence intervals should be justified so that parentheses displayed on consecutive lines of a table "line up".
- Boundary values of confidence intervals should be separated by a comma.
- Boundary values should be padded as necessary to accept negative values and to allow alignment of the decimal place.
- An example is given below:  
 (-0.12, -0.10)  
 ( 9.54, 12.91)

P-values:

- P-values should be reported to three decimal places, except values <1.000 but >0.999 will be presented as '>0.999' (e.g., 0.9998 is presented as >0.999); and values <0.001 will be presented as '<0.001' (e.g., 0.0009 is presented as <0.001). Rounding will be applied after the <0.001 and >0.999 rule

Ratios:

- Ratios should be reported to one more decimal place than the original data.

Spacing:

- There must be a minimum of 1 blank space between columns (preferably 2)

Version Number: 1.7  
 Version Date: 21Mar2018

Denominators:

- If a different count other than the population count is used for a denominator (within the table) to calculate percentages, there should be a row in the table that identifies that number “n”.
- Alternatively, a footnote should be included in each table with percentages to indicate the denominator for percentages.

Missing values

- A “0” should be used to indicate a zero frequency.
- A blank will be used to indicate missing data in an end-of-text table or subject listing.

